12.1.5 Response and Stable Disease Duration (RECIST 1.1 and iRECIST)

Response duration will be measured from the time measurement criteria for CR/PR or iCR/iPR (whichever is first recorded) are first met until the first date that recurrent or PD is objectively documented, taking as reference the smallest measurements recorded on study (including baseline).

Stable disease duration will be measured from the time of start of treatment until the criteria for progression are met, taking as reference the smallest sum on study (including baseline).

12.1.6 Methods of Measurement

The same method of assessment and the same technique should be used to characterize each identified and reported lesion at baseline and during follow-up. Assessments should be identified on a calendar schedule and should not be affected by delays in therapy. While on study, all lesions recorded at baseline should have their actual measurements recorded at each subsequent evaluation, even when very small (*e.g.*, 2 mm). If it is the opinion of the radiologist that the lesion has likely disappeared, the measurement should be recorded as 0 mm. If the lesion is believed to be present and is faintly seen but too small to measure, a default value of 5 mm should be assigned. For lesions which fragment/split add together the longest diameters of the fragmented portions; for lesions which coalesce, measure the maximal longest diameter for the "merged lesion."

Clinical Lesions. Clinical lesions will only be considered measurable when they are superficial and ≥ 10 mm as assessed using calipers (*e.g.*, skin nodules). For the case of skin lesions, documentation by color photography including a ruler to estimate the size of the lesion is recommended. If feasible, imaging is preferred.

Chest X-Ray. Chest CT is preferred over chest X-ray, particularly when progression is an important endpoint, since CT is more sensitive than X-ray, particularly in identifying new lesions. However, lesions ≥ 20 mm on chest X-ray may be considered measurable if they are clearly defined and surrounded by aerated lung.

CT, MRI. CT is the best currently available and reproducible method to measure lesions selected for response assessment. This guideline has defined measurability of lesions on CT scan based on the assumption that CT slice thickness is 5 mm or less. When CT scans have slice thickness greater than 5 mm, the minimum size for a measurable lesion should be twice the slice thickness. MRI is also acceptable in certain situations (e.g., for body scans). Other specialized imaging or other techniques may also be appropriate for individual case (*Eur J Ca* 45:228-247, 2009). For example, while PET scans are not considered adequate to measure lesions, PET-CT scans may be used providing that the measures are obtained from the CT scan and the CT scan is of identical diagnostic quality to a diagnostic CT (with IV and oral contrast).

Ultrasound. Ultrasound is not useful in assessment of lesion size and should not be used as a method of measurement. If new lesions are identified by ultrasound in the course of the study, confirmation by CT is advised.

Endoscopy, Laparoscopy. The utilization of these techniques for objective tumor evaluation is not advised. However, they can be useful to confirm complete pathological response when biopsies are obtained or to determine relapse in trials where recurrence following complete response or surgical resection is an endpoint.

Tumor Markers. Tumor markers alone cannot be used to assess objective tumor response. If markers are initially above the upper normal limit, however, they must normalize for a patient to be considered in CR.

Cytology, Histology. These techniques can be used to differentiate between PR and CR in rare cases if required by protocol (for example, residual lesions in tumor types such as germ cell tumors, where known residual benign tumors can remain). When effusions are known to be a potential adverse effect of treatment (e.g., with certain taxane compounds or angiogenesis inhibitors), the cytological confirmation of the neoplastic origin of any effusion that appears or worsens during treatment when the measurable tumor has met criteria for response or stable disease is advised to differentiate between response or SD and PD.

13.0 DATA AND SAFETY MONITORING

In compliance with the Washington University Institutional Data and Safety Monitoring Plan, an independent Data and Safety Monitoring Board (DSMB) will be specifically convened for this trial to review toxicity data. A DSMB will consist of no fewer than 3 members including 2 clinical investigators and a biostatistician. DSMB members must be employed by Washington University, Barnes-Jewish Hospital, or St. Louis Children's Hospital. Like investigators, DSMB members are subject to the Washington University School of Medicine policies regarding standards of conduct. Individuals invited to serve on the DSMB will disclose any potential conflicts of interest to the trial principal investigator and/or appropriate university officials, in accordance with institution policies. Potential conflicts that develop during a trial or a member's tenure on a DSMB must also

be disclosed.

Until such a time as the first secondary site enrolls its first patient, a semi-annual DSM report to be prepared by the study team will be submitted to the Quality Assurance and Safety Monitoring Committee (QASMC) semi-annually beginning six months after study activation at Washington University (if at least one patient has been enrolled) or one year after study activation (if no patients have been enrolled at the six-month mark).

The DSM report for the DSMB will be prepared by the study team with assistance from the study statistician, will be reviewed by the DSMB, and will be submitted to the QASMC Committee. The DSMB must meet at least every six months beginning six months after enrollment of the first patient at a secondary site, no more than one month prior to the due date of the DSM report to QASMC. This report will include:

- HRPO protocol number, protocol title, Principal Investigator name, data coordinator name, regulatory coordinator name, and statistician
- Date of initial HRPO approval, date of most recent consent HRPO approval/revision, date of HRPO expiration, date of most recent QA audit, study status, and phase of study
- History of study including summary of substantive amendments; summary of accrual suspensions including start/stop dates and reason; and summary of protocol exceptions, error, or breach of confidentiality including start/stop dates and reason
- Study-wide target accrual and study-wide actual accrual including numbers from participating sites
- Protocol activation date at each participating site
- Average rate of accrual observed in year 1, year 2, and subsequent years at each participating site
- Expected accrual end date, accrual by site
- Objectives of protocol with supporting data and list the number of participants who have met each objective
- Early stopping rules with supporting data and list the number of participants who have met the early stopping rules
- Summary of toxicities at all participating sites
- Abstract submissions/publications
- Summary of any recent literature that may affect the safety or ethics of the study

Further DSMB responsibilities are described in the DSMB charter.

The study principal investigator and coordinator will monitor for serious toxicities on an ongoing basis. Once the principal investigator or coordinator becomes aware of an adverse event, the AE will be reported to the HRPO and QASMC according to institutional guidelines (please refer to Section 8.0).

Refer to the Washington University Quality Assurance and Data Safety Monitoring Committee Policies and Procedures for full details on the responsibilities of the DSMB. This is located on the QASMC website at <https://siteman.wustl.edu/research/clinical-research-resources/protocol-office-prmcqasmc/>.

14.0 AUDITING

As coordinating center of this trial, Washington University (via the Quality Assurance and Safety Monitoring Committee (QASMC) will monitor each participating site to ensure that all protocol requirements are being met; that applicable federal regulations are being followed; and that best practices for patient safety and data collection are being followed per protocol. Participating sites will be asked to send copies of all audit materials, including source documentation. The audit notification will be sent to the Washington University Research Patient Coordinator, who will obtain the audit materials from the participating institution.

Notification of an upcoming audit will be sent to the research team one month ahead of the audit. Once accrual numbers are confirmed, and approximately 30 days prior to the audit, a list of the cases selected for review (up to 10 for each site) will be sent to the research team. However, if during the audit the need arises to review cases not initially selected, the research team will be asked to provide the additional charts within two working days.

Items to be evaluated include:

- Subject screening and enrollment
- Reporting of adverse events
- Maintenance of HIPAA compliance
- Completeness of regulatory documentation
- Completeness of participant documentation
- Acquisition of informed consent
- IRB documentation
- Issues of protocol adherence

Additional details regarding the auditing policies and procedures can be found at <https://siteman.wustl.edu/research/clinical-research-resources/protocol-office-prmcqasmc/>.

15.0 STATISTICAL CONSIDERATIONS

15.1 Study design

This is a single arm, multicenter, phase II study of of lenvatinib in combination with pembrolizumab (lenvatinib 20 mg/day + pembrolizumab 200mg q3weeks) in subjects with locally advanced or metastatic nccRCC who have not received any systemic therapy for stage IV RCC.

15.2 Endpoints

The primary endpoint is ORR, defined as the proportion of response-evaluable patients who have a best overall response (BOR) of either CR or PR, as graded by RECIST V1.1.

The secondary endpoints include:

- 1) Toxicity profiles and adverse events. The severity of AEs will be graded according to NCI Common Terminology Criteria for Adverse Events (CTCAE) v5.0.
- 2) Progression-Free Survival (PFS): defined as the time from date of first dose of study drugs to date of first documented disease progression or death to any cause or latest follow up, whichever occurs first.

If the disease recurrence/progression assessment involves more than one date, the earliest date will be used as the event date. A patient will be censored at the date of the last radiographic disease assessment indicating a lack of recurrence, if any of the following occurs before documented disease progression:

- Patient is alive and progression free at the time of analysis data cut-off.
- Disease progression or death occurs right after missing data for a scheduled radiographic disease assessment (including missing the assessment or assessment results in an in-evaluable status for overall response per RECIST 1.1).
- Patient receives non-protocol systemic anticancer treatment.
- Patients missing baseline disease assessment will be censored at date of receiving first drugs.
- For equivocal findings of progression (*e.g.*, very small and uncertain new lesions; cystic changes or necrosis in existing lesions), treatment may continue until the next scheduled assessment. If progression is confirmed at the next scheduled assessment, the date of progression should be the earlier date when progression was suspected.

- 3) Overall Survival (OS), defined as the time from the date of first dose of study drugs until date of death from any cause or latest follow up.

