1.0 SCHEDULE OF ACTIVITIES

Screening tests may take place no more than 21 days prior to the first day of study treatment. Window for study visits during treatment is +/- 7 days.

	Screening	C1D1	D1 of each subsequent cycle	Q9 wks	EOT	FU ⁴
Informed consent	X					
H&P, PS	X					
Vital signs	X		X			
CBC	X	X	X		X	
Blood chemistry ⁹	X		X			
Pregnancy test ¹	X ³					
TSH	X		X			
INR	X		X			
Urinalysis	X					
UPCR		X	X			
ECG	X					
CT or MRI ⁸	X			X	X	
Pembrolizumab		X	X			
Lenvatinib ²		X-----X ²				
Research tissue collection ⁷	X					
Research blood collection	X ⁵	X ⁵	X ⁶		X	
Adverse events	X-----X					
Progression and survival						X

1. Women of childbearing potential only
2. Lenvatinib is to be self-administered daily on each day of every 21-day cycle
3. Within 72 hours prior to first dose
4. After coming off treatment, patients will be followed every 12 weeks +/- 1 week until death for survival. If patients discontinue treatment prior to progression, patients will continue to be followed by scans approximately every 9 weeks until progression or the start of another anti-cancer therapy.
5. To be drawn at screening or C1D1 (up to 14 days prior to the start of treatment)
6. C4D1 only
7. Archival from within 3 months (preferred), up to 6 months acceptable; if no biopsy has been performed in the 6 months prior to treatment start then an SOC biopsy should take place after a patient has been determined to be eligible for the trial, if safe and feasible. See section 10.0 for more details.
8. Scans should continue every 9 weeks regardless of cycle length. See Section 12 for further instructions of timelines for obtaining confirmatory scans. For responses, or progression, a confirmatory scan should be performed at least 4 weeks after the initial scan showing progression or response.
9. Albumin, alkaline phosphatase, total bilirubin (and direct bilirubin if total bilirubin is above ULN), bicarbonate, BUN, calcium, chloride, creatinine, glucose, phosphorus, potassium, total protein, AST, ALT, sodium

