6.9 Lost to Follow-Up

A participant will be considered lost to follow-up if he or she fails to return for 2 scheduled visits and is unable to be contacted by the study team.

The following actions must be taken if the participant fails to return to clinic for a required study visit:

- The study team will attempt to contact the participant and reschedule the missed visit within 2 weeks and counsel the participant on the importance of maintaining the assigned visit schedule and ascertain if the participant wishes to and/or should continue in the study.
- Before a participant is deemed lost to follow-up, the investigator or designee will make every effort to regain contact with the participant (where possible, 3 telephone calls and, if necessary, a certified letter to the participant's last known mailing address). These contact attempts should be documented in the participant's medical record or study file.
- Should the participant continue to be unreachable, he or she will be considered to have withdrawn from the study with a primary reason of lost to follow-up.

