15.5 Population for Analyses

- Safety Analysis set: refers to the set of participants who take at least one dose of the study interventions and will be used for safety analysis.
- Efficacy Analysis set: refers to the participants who take at least two cycles of the combined study interventions and have baseline and at least one tumor assessment after receiving treatments unless discontinued due to disease progression, death or toxicity. Subjects received less than 2 cycles of combination treatments will be replaced with additional participants. Efficacy analysis set will be used as the primary set for ORR and other efficacy endpoints.
- Per-Protocol Analysis set: refers to the participants who follows the protocol without major violation and have received at least 80% of the targeted dosage. This set will be used for sensitivity analyses of the efficacy endpoints.

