15.6.3 Analysis of Secondary Endpoint(s)

PFS and OS will be analyzed using Kaplan-Meier product-limit estimates. Median PFS and OS and the cumulative probability of PFS at 3, 6, and 12 months and cumulative probability of OS at 6, 12, and 18 months will be presented with two-sided 95% confidence interval (CI) if estimable. PFS censoring rules will follow Food and Drug Administration (FDA) Guidance for Industry, Clinical Trial Endpoints for the Approval of Cancer Drugs and Biologics (2007). The KM

estimates of cumulative PFS and OS will be plotted over time with 95% CI if estimable.

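### Section 15.2 censors PFS when progression or death follows a single missed or inevaluable scan, which biases 6- and 12-month PFS upward where scans are missed, and its lead-in leaves the rule's reach unclear

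*Combined protocol and SAP*

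**What the plan says.** The Synopsis and Section 3.0 define PFS as time from first dose to the first documented progression or death. Neither makes an exception for missed scans.

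Section 15.2 adds censoring rules. Its lead-in says "A patient will be censored at the date of the last radiographic disease assessment indicating a lack of recurrence". It then attaches a condition to the whole list that follows: "if any of the following occurs before documented disease progression". One bullet in the list is "Disease progression or death occurs right after missing data for a scheduled radiographic disease assessment", with missing data described as "including missing the assessment or assessment results in an in-evaluable status for overall response per RECIST 1.1". The wording refers to one scheduled assessment, so a single gap is enough. A scan that was done but is inevaluable counts as a gap.

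Section 15.6.3 plans Kaplan-Meier medians and 3-, 6- and 12-month PFS. It adds that "PFS censoring rules will follow Food and Drug Administration (FDA) Guidance for Industry", but restates no rule. The only sensitivity analysis planned for efficacy is the per-protocol set in Section 15.5: "This set will be used for sensitivity analyses of the efficacy endpoints".

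On scan timing, Section 1.0 says "Scans should continue every 9 weeks regardless of cycle length" and gives a 7-day visit window either way. Section 6.9 has staff try to "reschedule the missed visit within 2 weeks".

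**The concern.** Kaplan-Meier estimation needs censoring that is unrelated to the event. Here the event decides it. Of two patients who each miss one scan, the one found progression-free at the next scan stays in the risk set, and the one who has progressed or died is moved back to an earlier date and censored. Events are removed selectively, so the curve is too high even when scans are missed purely at random. Deaths have known dates, so uncertainty about timing is no reason to discard them.

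The reach of the rule is also unclear. The lead-in requires the trigger to come before documented progression, yet this bullet's trigger includes progression. By the bullet's own words, progressions and deaths are both censored. By the lead-in taken literally, a progression documented at the next scan still counts, and only deaths (or undocumented progressions) are censored. Two analysts could report different PFS from the same data.

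The trial has one arm, so no control group shares the bias, and Section 2.2 gives the historical PFS values that readers will compare against.

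**Working it through.** The plan states no PFS figure to reproduce, so the check is of mechanism and size.

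**Inputs from the documents.** Scans every 9 weeks, with a window of 1 week either way (1.0); about 34 patients (15.4); landmarks at 3, 6 and 12 months (15.6.3); median PFS of 8.1 months, the sunitinib value in 2.2.

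**Assumptions, not in the documents.** Exponential PFS; 20% of events are deaths without prior progression; median survival after progression of 30 weeks; each scan missed or inevaluable independently at 0%, 2%, 5% or 10%. Rescheduling (6.9) and the visit window (1.0) point to the lower rates.

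**Mechanism.** With miss rate m, a progression after the first scan interval is counted only if the scan before it and the scan that should detect it are both usable, which has probability (1 − m)². The share of such events lost is:

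- m = 2%: 1 − 0.98² = 4.0%
- m = 5%: 1 − 0.95² = 9.8%
- m = 10%: 1 − 0.90² = 19.0%

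**Simulation, 400,000 patients per scenario, 12-month PFS.**

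| Missed | Events counted | Progressions and deaths censored | Deaths only censored | Censored only after 2 misses |
|---|---|---|---|---|
| 2% | 0.399 | 0.406 | 0.401 | 0.399 |
| 5% | 0.401 | 0.419 | 0.406 | 0.401 |
| 10% | 0.403 | 0.441 | 0.414 | 0.406 |

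The shifts from counting events are 0.7, 1.8 and 3.8 points when progressions and deaths are censored, and 0.2, 0.5 and 1.1 points for deaths only. With no scans missed there is no change. The two readings differ from each other by 0.5, 1.3 and 2.7 points.

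**Other landmarks.** 6-month PFS, events counted against progressions and deaths censored, is 0.672 v 0.675, 0.673 v 0.680 and 0.679 v 0.693: shifts of 0.3, 0.7 and 1.4 points. 3-month PFS hardly moves (0.834 v 0.830 at 10% missed).

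**Scale.** With 12-month PFS near 0.40 and n = 34, the 95% half-width is 1.96 × √(0.40 × 0.60 / 34) = 0.165, or 16.5 points. About 34 × 0.60 = 20 events are expected by 12 months. The rule loses 0.6, 1.4 and 2.6 of them (progressions and deaths) or 0.1, 0.4 and 0.7 (deaths only). In 4,000 simulated trials of 34 patients, with progressions and deaths censored, the 12-month estimate rose in 43%, 74% and 92% of trials and fell in 6%, 8% and 4%.

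**Other medians quoted in the documents.** 12-month PFS, events counted against progressions and deaths censored, at 10% missed: 5.6 months, 0.271 v 0.303; 6.7 months, 0.333 v 0.369; 17.7 months, 0.661 v 0.694.

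**Cross-check.** A separately coded simulation with scans exactly every 9 weeks, no deaths before progression and a median of 8.1 months gave 0.417 v 0.441 at 5% missed and 0.420 v 0.468 at 10%: shifts of 2.4 and 4.8 points. Without deaths, the first simulation gave 0.411 v 0.431 and 0.414 v 0.456: 2.0 and 4.2 points. Direction and approximate size agree.

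No claim is made about the median, because its shift depends on where the true median falls relative to the scan dates.

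**The case against.** The strongest reply concerns weight. PFS is a descriptive secondary endpoint with no test or threshold. At 2% to 5% missed, the rates best supported by the protocol's rescheduling and visit windows, the 12-month shift is about 1 to 2 points against a half-width of 16.5. All of this stands.

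A rescheduled scan may not count as missing. Confirmatory and end-of-treatment scans were not modelled, and a clean extra scan after a miss would stop a later progression from being censored, so the figures may be somewhat high for a given miss rate. That also stands. Rescheduling does not, however, help with a scan that was attended but inevaluable: under the response table in Section 12.1.3, incompletely evaluated target lesions without progression elsewhere give a not-evaluable result.

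The deaths-only reading can be called strained, because the bullet names progression. That is fair, but the lead-in says what it says. Section 15.6.3 may settle the matter by reference to the guidance; its text is not in the documents, so this cannot be checked, and an analyst working from the plan alone has two readings.

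Finally, counting late-detected progressions is not free of bias: in the cross-check it gave 0.420 at 10% missed, against 0.411 with no scans missed. Scan spacing alone lifts 12-month PFS from a true 0.358 to about 0.40, but it does so under every rule and cancels in the comparison. A two-miss rule keeps some event-triggered censoring, with a shift of at most 0.3 points at these rates. These points limit what the fix achieves; they do not favour the one-scan rule.

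**Conclusion.** The concern holds. Where scans are missed or inevaluable, the one-scan rule raises 6- and 12-month PFS, and the text does not say clearly whether it covers progressions and deaths or deaths only. On the assumptions above, the 12-month excess is about 1, 2 and 4 points at 2%, 5% and 10% missed on the wider reading, and 0.2, 0.5 and 1.1 points on the narrower one. It is zero if no scan is missed. The true miss rate is unknown, so these are ranges and not predictions.

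The shift is well inside the sampling error of a trial this size, but it goes in the favourable direction, and the per-protocol analysis changes the patients and not the censoring rule. The ORR decision rests on responder counts and is untouched. The change should be made, though it is not critical. Confidence is medium because the size depends on assumed rates.

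**What to change.** In Section 15.2:

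- When only one scheduled assessment is missing or inevaluable, count progression or death as an event on its documented date.
- State a separate rule for two or more consecutive missing assessments, for example censoring at the last evaluable progression-free scan.
- Reword the lead-in so that it no longer conflicts with a bullet whose trigger is progression or death.
- Keep the one-scan censoring rule as a named sensitivity analysis, and say whether it covers progressions and deaths or deaths only.

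In Section 15.6.3, refer to the rules in 15.2.

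The cost is three or four sentences and one extra Kaplan-Meier run, with no new data. The reported PFS figures will be slightly lower, and a progression found after one missed scan may be dated up to one 9-week interval late.
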